More recently, Sauer⁶³ et al. published on 3 patients with Shwachman-Diamond Syndrome who received treosulfan (12 g/m²/d x 3), fludarabine (30 mg/m²/d x 6), and Melphalan (140 mg/m²/d x 1) in combination with CAMPATH-1H (0.1 mg/kg x 2) in 2 cases and ATG in one case followed by HLA-identical sibling (n=1), HLA-matched unrelated donor (n=1) or 9/10 matched unrelated cord blood graft. All patients engrafted at 24, 31, and 26 days after HCT and had 100% donor chimerism at last follow up. Two of the 3 patients are alive at 9 and 20 months after HCT. The third patient who received a cord blood graft died 3 months after HCT of IPS. Greystoke and colleagues recently published a retrospective analysis of 32 pediatric patients undergoing HCT for nonmalignant diseases including primary immunodeficiency (n=18), metabolic disorders (n=9), osteopetrosis (n=4) and thalassemia (n=1).⁶⁴ Patients received a total treosulfan dose of 36 g/m² (n=6) or 42 g/m² (n=26) given in three divided doses on consecutive days. A variety of other conditioning agents were used depending on the stem cell source and donor type including fludarabine (150 mg/m²) Cyclophosphamide (200 mg/m²), plus or minus Campath or ATG. HLA-matched or mismatched related or unrelated bone marrow (n=17), peripheral blood (n=9), and cord blood (n=5) grafts were used as the stem cell source. Post HCT immunosuppression included Cyclosporine alone or combined with Mycophenolate Mofetil, methylprednisolone, or methotrexate. Twenty eight patients (87.5%) established donor cell engraftment; however, 4 patients have required additional transplantation procedures to maintain adequate donor derived hematopoiesis. With a median follow up of 471 days, 27 (84%) of the patients survive. One patient died early (day +4) due to sinusoidal obstructive syndrome and four other deaths were late due to disease progression, GVHD or infection. The incidence of GVHD was very low with 6 (19%) patients developing acute grade II (n=4) or grade III (n=2) acute GVHD and 4 (13%) patients developing chronic GVHD. Although multiple different donors and conditioning regimens were used, these results are encouraging in pediatric patients with nonmalignant disorders.

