The FHCRC PI and research staff will meet regularly to review all reported events. If the event meets FHCRC IRB current reporting obligations, it will be sent to the FHCRC IRB. After the FHCRC IRB has reviewed the event report it will be disseminated to all participating sites/investigators, the DSMB, and the study sponsor.

When a patient experiences disease recurrence or graft failure and goes on to further treatment off protocol, adverse events will no longer be collected with the exception of death.

Patients enrolled in this study are receiving treatments that are generally associated with high rates of expected adverse events (outlined in **Appendix I**).

17.F. Reporting to Coordinating Center and Fred Hutch IRB

For patients being cared for at the FHCRC, health care providers communicate with the PI or research staff as events occur triggering subsequent reporting. For patients not being cared for at the FHCRC the outside facilities communicate with the PI or research study staff for these reporting purposes.

As FHCRC is the coordinating center, all reportable events will be collected by the FHCRC PI and/or study staff for submission to FHCRC IRB. All reportable events should be submitted to the coordinating center on the relevant FHCRC IRB forms. (See **Tables 2 and 3** for FHCRC IRB Reporting Policies and Forms for Reporting)

Table 2 FHCRC IRB Policies for Reportable Events (Relevant FHCRC policies include, but are not limited to the following documents. Please also refer to the FHCRC IRO website.)

| | | |
|-----------------|--|---|
| IRB Policy 2.6 | Unanticipated Problems Involving Risks to Subjects or Others (Adverse Events) | http://extranet.fhcrc.org/EN/sections/iro/irb/ae.html |
| IRB Policy 1.9 | Noncompliance with the Office of the Director's Human Research Protection Program Policy | http://extranet.fhcrc.org/EN/sections/iro/irb/ae.html |
| IRB Policy 1.11 | Reporting Obligations for Principal Investigators | http://extranet.fhcrc.org/EN/sections/iro/irb/policy/ |
| IRB Policy 2.2 | Continuing Review | http://extranet.fhcrc.org/EN/sections/iro/irb/policy/index.html |
| IRB Policy 1.13 | Investigational New Drugs (IND), Biologics and Investigational Device Exemptions (IDE) | http://extranet.fhcrc.org/EN/sections/iro/irb/policy/index.html |

Table 3 Fred Hutch IRB Forms for Reporting

| | |
|--|---|
| Adverse Event Reporting Form | http://extranet.fhcrc.org/EN/sections/iro/irb/forms/index.html |

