19. STATISTICAL CONSIDERATIONS AND TERMINATION OF STUDY

The primary objective of this clinical trial is to evaluate, within the limits of a phase II study, the preliminary efficacy as defined by engraftment, of a regimen consisting of treosulfan and fludarabine followed by allogeneic HCT in patients with nonmalignant inherited disorders. We plan to enroll at least 30 patients on this study. A minimum of 30 patients will be enrolled onto Arm A. The protocol will continue to accrue until this goal is met. There will be no set limit for Arm B: the cord blood arm. Analyses will be carried out separately between Arm A and B. We will be encouraged to continue study of this treatment if at least 27 of 30 patients engraft. Table 5 shows the probability of observing 27 or more successes among 30 patients for several possible true rates of engraftment.

The protocol was modified in January 2011 and September 2011. Due to a higher than anticipated incidence of acute grade III-IV GVHD for both arms in the first 13 patients (5/13 = 38%; 3/8 bone marrow recipients, 2/5 cord blood recipients) the protocol was modified to add rabbit ATG (thymoglobulin) to both arms initially for unrelated recipients (January 2011) and subsequently for the related recipients (September 2011). In addition, due to graft rejection (n=1) and low donor chimerism/inadequate disease response (n=1) in 2 of the 5 patients enrolled onto the cord blood arm, the cord blood arm was modified to increase the TBI from 200 cGy to 300 cGy TBI for non T-cell deficient patients. The revised protocol will reset the target accrual to at least 30 patients as of January 2011, with a minimum enrollment of 30 onto Regimen A (as stated above). The efficacy analysis will be performed separately for the initial 13 patients (Regimen A: n=8, Regimen B: n=5) and those accrued under the modified regimen. Only patients enrolled after this protocol modification will be counted towards the stopping rules.

Table 5. Probability of observing 27 or more successes in 30 patients

| True rate of engraftment | Pr(\geq 27 successes) |
|--------------------------|--------------------------|
| 70% | 0.01 |
| 80% | 0.12 |
| 90% | 0.65 |
| 95% | 0.94 |

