| Number of patients | True rate of event | Probability of stopping |
|--------------------|--------------------|-------------------------|
| 10 | 15% | 0.03 |
| 15 | 15% | 0.04 |
| 20 | 15% | 0.04 |
| 25 | 15% | 0.05 |
| 10 | 35% | 0.32 |
| 15 | 35% | 0.49 |
| 20 | 35% | 0.54 |
| 25 | 35% | 0.63 |
| 10 | 45% | 0.57 |
| 15 | 45% | 0.78 |
| 20 | 45% | 0.84 |
| 25 | 45% | 0.91 |

The incidence of graft rejection will also be monitored in all patients. Regimen A and B will be monitored/analyzed separately. If there is sufficient evidence to suggest that the true incidence of graft rejection exceeds within the first 365 days 10% on either arm, enrollment will be suspended on that arm and the DSMB will be convened to make recommendations regarding protocol modification and/or dose escalation. Sufficient evidence will be an observed rate of graft rejection that corresponds to a one-sided 80% confidence interval with a lower limit greater than 10%. These limits will be examined after every 5th enrolled patient becomes eligible for evaluation. In practice, the study arm will be suspended if we observe the following number of graft rejections in study patients: 2/5, 3/10, 3/15, 4/20, 5/25, 5/30, 6/35, 7/40, 7/45 or 8/50 per disease subgroup per study arm (Regimen A versus Regimen B). Table 7 summarizes the operating characteristics of this stopping rule for enrollment of up to 50 patients per disease subgroup, as estimated from 5,000 Monte Carlo simulations.

Table 7. Probability of stopping the trial for excess graft rejection

| Number of patients | True rate of event | Probability of stopping |
|--------------------|--------------------|-------------------------|
| 10 | 5% | 0.03 |
| 15 | 5% | 0.05 |
| 20 | 5% | 0.05 |
| 25 | 5% | 0.05 |
| 10 | 20% | 0.38 |
| 15 | 20% | 0.62 |
| 20 | 20% | 0.68 |
| 25 | 20% | 0.72 |
| 10 | 30% | 0.67 |
| 15 | 30% | 0.88 |
| 20 | 30% | 0.93 |
| 25 | 30% | 0.95 |

Therefore, **stopping rules** will be imposed for:

Day 200 TRM > 25% (3/5, 5/10, 6/15, 8/20, 9/25, 10/30, 12/35, 13/40, 15/45, 16/50) per disease subgroup per study arm (Regimen A versus Regimen B).

Day 365 Graft rejection (defined as CD3 T cell chimerism < 5%) > 10% (2/5, 3/10, 3/15, 4/20, 5/25, 5/30, 6/35, 7/40, 7/45, 8/50) per disease subgroup per study arm (Regimen A versus Regimen B)

Day 100 Grade III/IV GVHD >15% for Arm A +rATG PBSC grafts 2/5, 3/10, 4/15, 5/20, 6/25, 7/30, 8/35, 9/40, 10/45, or 11/50

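### The graft rejection stopping rule counts only donor CD3 below 5%, so a second transplant given for a failing graft before that point is not counted

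*Combined protocol and SAP*

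**What the plan says.** Section 19 monitors graft rejection separately in each regimen and, in Regimen A since the 2015 modification, in each disease subgroup. The condition is "If there is sufficient evidence to suggest that the true incidence of graft rejection exceeds within the first 365 days 10% on either arm". Evidence is sufficient when the observed rate gives a "one-sided 80% confidence interval with a lower limit greater than 10" per cent. The limits are "2/5, 3/10, 3/15, 4/20, 5/25, 5/30, 6/35, 7/40, 7/45 or 8/50 per disease subgroup", and "These limits will be examined after every 5th enrolled patient becomes eligible for evaluation". Reaching a limit suspends enrolment and convenes the DSMB.

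The event itself is defined only in the summary of stopping rules: "Day 365 Graft rejection (defined as CD3 T cell chimerism < 5%) > 10" per cent. Nothing else in section 19 makes a second transplant an event, ends follow-up of the first graft at a second one, or excludes chimerism measured afterwards.

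Three other places bear on this:

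- Section 17E describes a patient who has "disease recurrence or graft failure and goes on to further treatment off protocol". It then rules only that adverse events are no longer collected, apart from death.
- Section 19, on the cord blood arm, reports a change made "due to graft rejection (n=1) and low donor chimerism/inadequate disease response (n=1) in 2 of the 5 patients". Low chimerism is thus named apart from rejection.
- Section 11, Regimen B, treats donor T-cell chimerism below 40% as a possible warning of rejection, well above the 5% event threshold.

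**The concern.** The rule is there to detect grafts that fail. A second transplant for a failing graft is direct evidence of failure, yet the written definition does not use it.

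Take a hypothetical patient whose donor CD3 falls from 40% to 12% and who has a second transplant for graft failure on day 130. CD3 never went below 5% on the first graft, so no event is recorded. Samples taken later in the first year may show high donor CD3 that belongs to the second graft. The patient then stands in the denominator as someone without rejection.

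This does not depend on which cell lineage is measured. It arises even when CD3 is the failing lineage, because the second transplant can come before the threshold. The error runs one way: the more often failing grafts are replaced early, the fewer events the rule sees. The subgroup target is a minimum of 20 patients and the limit there is 4 of 20, so one uncounted patient can decide whether enrolment is suspended.

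**Working it through.** **Inputs from section 19.** Tolerated rate 10% by day 365; one-sided 80% confidence; looks every 5 patients; limits 2/5, 3/10, 3/15, 4/20, 5/25, 5/30, 6/35, 7/40, 7/45, 8/50; Table 7. **Assumption, not in the documents:** *f*, the share of graft failures that receive a second transplant while CD3 is at least 5% and never later read below 5%. The range shown is 0%, 10%, 25% and 50%.

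**1. The limits.** A limit of *x* in *n* meets the criterion when P(X ≥ *x*) at a 10% rate is below 0.20. For *n* = 5:

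- P(X ≥ 1) = 1 − 0.9⁵ = 0.41, not enough.
- P(X ≥ 2) = 1 − 0.9⁵ − 5(0.1)(0.9⁴) = 1 − 0.590 − 0.328 = 0.08, enough.

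So the limit is 2/5. All ten published limits equal the exact (Clopper-Pearson) ones.

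**2. Table 7.** The stopping probability is an exact binomial recursion. At each look, add the five new patients' events, count the paths at or above the limit as stopped, and carry the rest forward. For a 20% rate the first look gives 1 − 0.8⁵ − 5(0.2)(0.8⁴) = 1 − 0.328 − 0.410 = 0.26. Continuing through later looks:

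| True rate | n=10 | n=15 | n=20 | n=25 |
|---|---|---|---|---|
| 5%, Table 7 | 0.03 | 0.05 | 0.05 | 0.05 |
| 5%, recomputed | 0.028 | 0.049 | 0.052 | 0.053 |
| 20%, Table 7 | 0.38 | 0.62 | 0.68 | 0.72 |
| 20%, recomputed | 0.389 | 0.624 | 0.687 | 0.725 |
| 30%, Table 7 | 0.67 | 0.88 | 0.93 | 0.95 |
| 30%, recomputed | 0.669 | 0.882 | 0.926 | 0.949 |

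All 12 cells agree within 0.01. The arithmetic of the plan is sound; the question is what counts as an event.

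**3. Effect of uncounted failures.** Counted rate = true failure rate × (1 − *f*). The same recursion at the counted rate gives P(stop by 20):

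| *f* | True 20%: counted rate | P(stop by 20) | True 30%: counted rate | P(stop by 20) |
|---|---|---|---|---|
| 0% | 20% | 0.69 | 30% | 0.93 |
| 10% | 18% | 0.61 | 27% | 0.88 |
| 25% | 15% | 0.47 | 22.5% | 0.77 |
| 50% | 10% | 0.23 | 15% | 0.47 |

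**4. Cost of a wider event with the same limits.** Suppose the event rate is 5% on CD3 alone and 10% once second transplants are added (assumption). P(stop by 20) goes from 0.05 to 0.23, and P(stop by 50) from 0.06 to 0.33.

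**The case against.** The strongest reply is that a CD3 threshold is objective, whereas a second transplant depends on clinical judgement, and that nothing shows the gap to be large. Much of this stands.

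- **Frequency.** No passage says a second transplant is given while CD3 is still at least 5%. Section 17E describes failure first and treatment after, so it shows that further treatment is foreseen, not that it pre-empts the threshold. At *f* = 0 nothing changes.
- **The cited paediatric treosulfan series.** Section 3C.2b reports that "4 patients have required additional transplantation procedures to maintain adequate donor derived hematopoiesis". A reader might infer that 4/32 = 12.5% already exceeds the 10% limit. The documents do not support that comparison: they give no CD3 level, no timing (median follow-up was 471 days) and no type of procedure, and the series mixed conditioning regimens and graft sources.
- **Chimerism summaries.** A reader might infer that second-graft samples contaminate the chimerism endpoint. The stated objective in section 4B is chimerism at days +28 and +100, and a second transplant on day 130 leaves both samples on the first graft.
- **Primary criterion.** A reader might also infer that rescued patients inflate the 27-of-30 criterion. Section 19 does not define engraftment for that criterion, so this cannot be established.
- **Never counted.** This would be too strong. CD3 may still fall below 5% within 365 days, for example if the second graft also fails.
- **Oversight.** Under section 17A the DSMB reviews all outcome data twice a year. The protocol has also been changed for low chimerism and for poor engraftment without citing the rejection limit.

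The oversight argument only goes so far: noticing a case informally does not count it toward the limit. Nor does the objectivity of CD3 answer the miscounting of a first graft that has been replaced.

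**Conclusion.** The point holds as a gap in the counting rule. Section 19 gives one explicit event definition. Applied exactly, it scores a patient as free of rejection when the first graft has failed and been replaced with CD3 at or above 5%, unless CD3 later falls below 5%.

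The size cannot be known from the documents. Over an assumed missed share of 0% to 50%, P(stop by 20) runs from 0.69 down to 0.23 at a true 20% failure rate, and from 0.93 down to 0.47 at 30%. These figures assume independent patients, looks every 5 patients, and a missed share that does not vary with time or subgroup.

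Table 7 itself is not wrong. It is correct for the rate of CD3 below 5%; it does not describe sensitivity to graft failure in the wider sense. The change is worth making because the rule guards the outcome behind the primary objective and the remedy is small.

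**What to change.** In section 19, define the stopping event as:

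*Graft rejection by day 365: donor CD3 below 5%, or a second transplant given for graft failure or rejection of the first graft, whichever is first, dated at that event.*

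Add that only samples taken before the second graft are used to judge rejection and engraftment of the first. List boosts, donor lymphocyte infusions and second transplants given only for low or mixed chimerism separately for the DSMB, without counting them. This is a rule for counting events and says nothing about when to re-transplant.

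Keep the numerical limits, and state that the 10% tolerance now applies to the wider event.

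The costs should be written down:

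- The wider event is reached sooner. The increase from 0.05 to 0.23 by 20 patients, and from 0.06 to 0.33 by 50, shows the scale if the event rate doubles from 5% to 10%. The consequence is suspended enrolment and DSMB review.
- The event gains an element of judgement. The date, type and stated reason for each second infusion must therefore be recorded; the documents do not show that the reason is now collected.

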The incidence of day 200 transplant-related mortality (TRM) will be monitored in all patients. If there is sufficient evidence suggesting that the true incidence of day 200 TRM exceeds 25% on either arm, enrollment on that arm will be suspended and the DSMB will be convened to make recommendations regarding protocol modification. Sufficient evidence will be an observed rate of day 200 TRM that corresponds to a one-sided 80% confidence interval with a lower limit greater than 25%. These limits will be examined after every 5th enrolled patient becomes eligible for evaluation. In practice, the study arm will be suspended if we observe the following number of TRM in study patients: 3/5, 5/10, 6/15, 8/20, 9/25, 10/30, 12/35, 13/40, 15/45 or 16/50 per disease subgroup per study arm (Regimen A versus Regimen B). Table 6 summarizes the operating characteristics of this stopping rule, for enrollment of up to 50 patients per disease subgroup per study arm (Regimen A versus Regimen B) as estimated from 5,000 Monte Carlo simulations. We will apply stopping rules to regimens A and B separately.

The protocol related to regimen B was modified in April 2012. Stopping rules for excess day 200 TRM were met in October 2011 due to 3 deaths occurring in the 5 patients enrolled since the January 2011 protocol modifications (1 due to multi-system organ failure; 1 due to ARDS/diffuse alveolar damage; and 1 due to gram positive sepsis (strep viridans) with multi-system organ failure, questioned possible sinusoidal obstructive syndrome/veno-occlusive disease). All deaths occurred before day 100, with two very early on post-transplant day 1 and day 7. However, the causes of death did not appear to be related to any single part of the regimen. The Data Safety Monitoring Board met and reviewed the data and recommended the following: The revised protocol will allow up to 5 more patients to be enrolled on regimen B before reconvening the DSMB, with each patient enrolled no sooner than 28 days following the date of transplantation (defined as the date of stem cell infusion) of the previous patient. The stopping rules for this arm (Regimen B) were not reset and will continue as stated in the protocol. The next stopping rule would be triggered at 5/10. Therefore, if 2 of the next 5 patients enrolled dies on Regimen B (cord blood), the stopping rule would be triggered and the DSMB will reconvene.

Table 6. Probability of stopping the trial for excess day 200 TRM

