The dosing of treosulfan on protocol 2256 was modified in June 2013, specifically the dose of Treosulfan was decreased for smaller children. However, three of the first five patients treated with the reduced dose have experienced poor engraftment. Therefore the original dose of treosulfan was reinstated in April 2014. The protocol accrual will continue to a total of 60 patients in Arm A with Treosulfan/Fludarabine/rATG, so as to ensure adequate numbers of smaller children will be treated at the original dose, since among the original 30 patients only a small number were <0.5 m² body surface area. As stated above, the initial 8 patients transplanted on Regimen A with Treosulfan and fludarabine only do not count towards the accrual goal of 60. Therefore the total number of patients accrued on Regimen A will be 68. The same stopping rules for TRM and rejection applied to the first 30 patients in Arm A will be applied separately to the additional 30 patients in Arm A; however, accrual to Arm B will continue as before under the same stopping rules.

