In October/November 2015 Regimen A of the protocol was modified to increase accrual to a minimum of 20 patients for each subgroup of patients (for example, primary immunodeficiency diseases, hemophagocytic disorders, hemoglobinopathies, and marrow failure disorders) who receive Treosulfan, fludarabine, and rabbit ATG. The protocol will continue to accrue until a minimum of 20 patients are in each subgroup, in order to better evaluate the safety and effectiveness of the regimen in each subgroup. There is no limit to the overall accrual to Regimen A as long as the minimum of 20 patients per subgroup has not been reached and each subgroup will continue to accrue until all subgroups reach a minimum of 20 patients. We estimate the overall accrual will be 100-120 patients. Stopping rules for TRM and graft rejection will be applied separately in each disease subgroup of patients who receive Treosulfan, fludarabine, and rabbit ATG conditioning. There are additional patients with nonmalignant diseases that do not fit into one group that have enrolled onto the protocol and will continue to enroll onto the protocol such as metabolic disorders, autoimmune disorders, or other rare nonmalignant diseases. We will continue to enroll these patients but they will not count towards the stopping rules or enrollment since we do not anticipate very many of these patients. However, they will be reviewed by the data safety monitoring board. Accrual to Arm B will continue as before under the same stopping rules.

In March 2017, the protocol was modified to allow the use of both bone marrow and cord blood from the same HLA-matched sibling donor. Specifically, at the discretion of the PI, bone marrow and cord blood cells from the same HLA-matched sibling donor may be used together for transplantation in cases where such cord blood cells were previously stored. The patients enrolled onto the protocol who receive both bone marrow and cord blood from the same HLA-matched sibling donor will be enrolled onto Regimen A of the protocol and analyzed with this group.

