In March 2018, the protocol was modified to prioritize PBSC (Regimen A) as the preferred stem cell source when feasible. This change was made with the goal of improving donor chimerism. PBSC has a higher risk of graft versus host disease; therefore, a stopping rule for grade III-IV GVHD will be added to the protocol – Regimen A only. Since bone marrow will still be allowed on Regimen A, we will apply this stopping rule to PBSC transplants. If there is sufficient evidence to suggest that the true incidence of grade III-IV GVHD at day 100 exceeds 15% (Regimen A), enrollment will be suspended on that arm and the DSMB will be convened to make recommendations regarding protocol modification. The stopping rule would be triggered if 2 of 5, 3 of 10, 4 of 15, 5 of 20, 6 of 25, 7 of 30, 8 of 35, 9 of 40, 10 of 45, or 11 of 50 experience grade III-IV GVHD. This stopping rule will not be by disease subgroup but for all PBSC transplants. The current PBSC transplants on the protocol will be included in this stopping rule.

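### In Regimen A, patients outside the disease subgroups keep enrolling but count towards no TRM or graft-rejection limit, so a problem confined to them can reach no numeric trigger

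*Combined protocol and SAP*

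**What the plan says.** All the text is in Section 19 unless another section is named.

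- **General rule.** The TRM paragraph opens with "The incidence of day 200 transplant-related mortality (TRM) will be monitored in all patients" and the rejection paragraph with "The incidence of graft rejection will also be monitored in all patients".
- **Limits.** For TRM, "the study arm will be suspended if we observe the following number of TRM in study patients": 3/5, 5/10, 6/15, 8/20 and so on to 16/50. The rejection limits are 2/5, 3/10, 3/15, 4/20 and so on to 8/50. Both lists are given per disease subgroup per study arm and are examined after every fifth evaluable patient. A crossing suspends enrollment on the arm and convenes the DSMB.
- **2015 modification.** "Stopping rules for TRM and graft rejection will be applied separately in each disease subgroup of patients" who receive treosulfan, fludarabine and rabbit ATG. Four subgroups are listed as examples: primary immunodeficiency, hemophagocytic disorders, hemoglobinopathies and marrow failure. Each has a minimum accrual of 20.
- **Everyone else in Regimen A.** Patients who do not fit a group continue to enroll, but "they will not count towards the stopping rules or enrollment since we do not anticipate very many of these patients". The stated substitute is: "However, they will be reviewed by the data safety monitoring board".
- **2018 GVHD rule.** This rule covers all Regimen A PBSC transplants regardless of disease, and "The current PBSC transplants on the protocol will be included in this stopping rule".

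**The concern.** A patient outside the subgroups enters no numerator and no denominator for TRM or rejection. Three transplant-related deaths or two rejections in the first five patients of a named subgroup suspend enrollment. Five of five among the excluded patients would reach no limit. This also sits awkwardly with the two opening sentences, which describe the monitoring as covering every patient.

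The only reason given is that few such patients are expected. No number or separate cap is stated. The estimate of 100 to 120 for Regimen A need not include them, because they do not count towards enrollment.

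A problem specific to these diseases is plausible. Section 3B reports 37% transplant-related death by day 200 among 27 patients with metabolic storage disease, osteopetrosis or HLH. That followed older myeloablative conditioning, and the 27 include HLH patients, who now have a subgroup. The figure is therefore not a prediction for this regimen. It shows only that risk can differ by disease.

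**Working it through.** **1. Reproduce the limits.** The rule in Section 19 is a one-sided 80% lower confidence limit above 25% (TRM) or 10% (rejection). The exact (Clopper-Pearson) lower limit for x events in n is the p that solves P(X ≥ x | n, p) = 0.20. At n = 5:
- TRM: 3/5 gives 0.327 (> 0.25) and 2/5 gives 0.169 (not), so the limit is 3.
- Rejection: 2/5 gives 0.169 (> 0.10) and 1/5 gives 1 − 0.8^(1/5) = 0.044 (not), so the limit is 2.

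The same rule returns all ten TRM limits and all ten rejection limits.

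**2. Reproduce Tables 6 and 7.** I used an exact binomial recursion in place of the 5,000 simulations. At each look, add a Binomial(5, p) count to the paths that have not stopped, then remove and sum those at or above the limit. At the first look:
- TRM 35%: P(X ≥ 3) = 10(0.35³)(0.65²) + 5(0.35⁴)(0.65) + 0.35⁵ = 0.181 + 0.049 + 0.005 = 0.235.
- Rejection 20%: 1 − 0.8⁵ − 5(0.2)(0.8⁴) = 1 − 0.328 − 0.410 = 0.263 (unrounded terms).

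All 24 table entries reproduce to within 0.012. For example, TRM 35% at n = 20 gives 0.545 (Table 6: 0.54), and rejection 20% at n = 20 gives 0.687 (Table 7: 0.68). The limits are sound for the subgroups they cover.

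**3. Excluded patients as the plan stands.** They are in no count, so the probability that their events reach a limit is 0 at any true rate.

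**4. The same patients as one residual stratum.** The documents give no size for this group; 5 to 20 is an assumption. Cumulative trigger probability under the existing limits:

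| True rate | n = 5 | n = 10 | n = 15 | n = 20 |
|---|---|---|---|---|
| TRM 15% | 0.027 | 0.031 | 0.040 | 0.041 |
| TRM 25% (threshold) | 0.104 | 0.137 | 0.205 | 0.222 |
| TRM 35% | 0.235 | 0.332 | 0.496 | 0.545 |
| Rejection 5% | 0.023 | 0.028 | 0.049 | 0.052 |
| Rejection 10% (threshold) | 0.082 | 0.113 | 0.210 | 0.232 |
| Rejection 20% | 0.263 | 0.389 | 0.624 | 0.687 |

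**5. What the named subgroups already catch.** If the whole regimen has the problem, the chance that at least one of four subgroups of 20 triggers is:
- TRM 35%: 1 − (1 − 0.5453)⁴ = 0.957.
- Rejection 20%: 1 − (1 − 0.6867)⁴ = 0.990.

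**6. Cost in unneeded triggers, fifth stratum of 20.** TRM and rejection are treated as independent, as are the strata.
- TRM 15% and rejection 5% together, four strata: 1 − (0.9589 × 0.9478)⁴ = 0.32. Five strata: 1 − (0.9589 × 0.9478)⁵ = 0.38.
- TRM at the 25% threshold: 1 − (1 − 0.2221)⁴ = 0.63, rising to 1 − (1 − 0.2221)⁵ = 0.72.
- Rejection at the 10% threshold: 1 − (1 − 0.2322)⁴ = 0.65, rising to 1 − (1 − 0.2322)⁵ = 0.73.

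**The case against.** **The exclusion is open, reasoned and has a stated substitute.** A reader might infer that these patients are unmonitored. The documents do not support that. Section 17A has the DSMB meet twice a year and review all outcome data, and has the PI review each patient's outcomes on an ongoing basis. Table 4 requires fatal or life-threatening events to be notified within 24 hours. Section 17I recognises suspension by the PI, IRB, IND sponsor or DSMC. The PBSC GVHD rule can count these patients. All of this stands. What is missing is only a count that obliges suspension for TRM or rejection.

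**Monitoring a rate in every patient is not the same as counting every patient against a limit.** On that reading the later, specific text governs and there is no outright contradiction. This largely stands, so the remedy here is clearer wording.

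**A rule for a small group does little.** It is silent below five evaluable patients, and at five it detects TRM of 35% with probability only 0.24. That is correct. It also means the rule costs nothing if the group stays below five. If the group grows past five, the stated reason for the exclusion weakens.

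**Pooling runs against the reason for subgroups.** A residual stratum mixes unlike diseases, and a crossing such as 2/5 rejections would suspend Regimen A for everyone. This is a real cost and is counted above.

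**Subgroup membership.** Because the subgroup list is only illustrative, and the staging tables in Section 14 place HLH and sickle cell disease under a heading for other diseases, a reader might infer that an event could be assigned to a subgroup after it is known. The documents do not support this. Section 3A groups diseases under headings that include all four subgroups, and Section 3B also lists metabolic, red cell, osteopetrosis and HLH patients separately. The staging tables are test schedules. Appendix F records the diagnosis before transplant and is signed. What remains is that no document maps each diagnosis to a stratum.

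**Conclusion.** The point holds as a gap of limited scope. For Regimen A patients outside the subgroups, no count of day 200 transplant-related deaths or day 365 rejections can reach a pre-set limit, and suspension on those grounds rests on judgement. A regimen-wide excess would very probably show in the named subgroups, so what is exposed is an excess confined to these patients.

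The practical weight is unknown because the documents do not give the size of the group. The gain in trigger probability (to 0.24–0.55 at TRM 35% and 0.26–0.69 at rejection 20%) rests on the assumed sizes of 5 to 20 and on one common event rate within the stratum. The 0.957 and 0.990 also assume four subgroups of exactly 20 with equal rates. This is a change to consider, and it does not show that the plan is unsafe.

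**What to change.** 1. Keep these patients out of the minimum-20 accrual targets, but count them for safety as one residual Regimen A stratum under the TRM and rejection limits already stated. A crossing would suspend enrollment and convene the DSMB, as for the subgroups.
2. Include those already enrolled, following the 2018 precedent for existing PBSC transplants.
3. Reconcile the opening TRM and rejection sentences of Section 19 with the 2015 modification, so that it is clear who is monitored and who is counted.
4. List which diagnoses belong to each subgroup, and record the resulting stratum on the registration form (Appendix F) from the diagnosis already collected there.

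The work is wording, one form field and a tally of data already collected. The statistical cost is the higher chance of an unneeded suspension. For a stratum of 20 it rises from about 0.32 to 0.38 at acceptable rates of both events, and at the threshold rates from 0.63 to 0.72 (TRM) and from 0.65 to 0.73 (rejection). Because the stratum is mixed, a crossing prompts DSMB review but does not show which disease is affected.
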